3.1.1 PRACTICE LEVEL PROMOTION

Providers in the randomly selected group of treatment primary care practices will be encouraged to batch order blood glucose flowsheets for all patients with diabetes with active MyChart accounts. The research team will contact physicians and practice managers with an explanation of the initiative and instructions for completing batch orders and viewing entries through the system. The practice will be advised to complete filling orders over a two week administration period, after which the implementation period will begin. A batch order will trigger two forms of alerts sent to providers, according to the default settings for electronic glucose flowsheets:

1. A bi-weekly report received of values that the patient has entered, or a notification that the patient has not entered data during the interval.
2. A notification when patient entered values are out of range (the patient also gets a notification that their doctor will see this value) according to the following current settings:

Notification Setting	Current Default
Pre-Meal Range (entry outside range=alert)	60-180 mg/dl
Post-Meal Range	100-240 mg/dl
Nighttime Range	60-300 mg/dl

Patients will automatically be notified when the flowsheet has been ordered for them. Additionally, providers will be given text for a secure smart-text message to send to all patients receiving the flowsheets, instructing them to enter data for the study period. The secure message will also provide them with information on how to enter data, and on the benefits of tracking blood glucose. Draft text of this message is included below:

Dear [Patient],

You may have seen that there is a new electronic form available for you to enter your blood glucose results in the MyChart portal. Keeping track of your blood glucose can help you manage your diabetes and reduce your chances for developing complications like heart disease, kidney damage and eye damage. As part of a new Inova program to help patients with diabetes get healthy, I would like you to try entering the results of your home blood glucose tests on MyChart for the next 3 months, through [Date]. Please let me know if you have any questions.

Sincerely,

[Practitioner]

WHAT TO DO NEXT

1. **Get help:** If you need help learning how to measure your blood glucose or getting testing supplies, you can contact [Practice Contact].

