3.1.2 INDIVIDUAL LEVEL REMINDERS

After the initial two-week roll-out/administration period, follow-up emails will be sent out by the research team to patients at treatment practices whose doctors have placed blood glucose flowsheet orders. Patients will be assigned at the individual level to one of four reminder treatment conditions, which will be administered by the research team. The number of reminder conditions may be reduced (to 2 or 3 instead of 4) depending on the rate of flowsheet orders by physicians to preserve statistical power. Assignment to any of these treatments will not preclude or provide guidelines for other communication between providers and patients (e.g. providers are free to send out their own reminders or messaging regardless of patient assignment to treatment group). The four reminder treatment conditions are described below:

(1) No additional reminders from research group

(2) Standard secure message reminder, addressed from Inova Medical Group, sent every two weeks during 12 week implementation period. Draft text below:

*Dear [Patient],
Don't forget to track your blood glucose through MyChart! Keeping track of your blood glucose can help you manage your diabetes and reduce your chances for developing complications like heart disease, kidney damage and eye damage.
Sincerely,
Inova Medical Group*

(3) Secure message reminder with chance to receive gift card, addressed from Inova, sent every two weeks during 12 week implementation period. Draft text below:

*Dear [Patient],
You have been chosen for a special program to help you get started tracking your blood glucose through MyChart. For each day that you track your blood glucose on MyChart through [DATE], you will be*

entered to receive one of fifty \$50 gift cards to Amazon. You'll be sent a secure message through MyChart after [DATE] if you've been selected to receive a gift card. Keeping track of your blood glucose can help you manage your diabetes and reduce your chances for developing complications like heart disease, kidney damage and eye damage.

Sincerely,

Inova Medical Group

(4) Secure message reminder, addressed from primary care doctor, sent every two weeks during 12 week implementation period. Draft text below:

Dear [Patient],

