3.4 Endpoints/Outcomes Measurements

Hypothesis: Interfacing with primary care practices to encourage physicians to implement default online orders of blood glucose flowsheets and informational messaging for all patients with diabetes will increase patient adoption.

Outcome Measures: Comparison of individuals between treatment and control practices-- (a) fraction of patients entering blood glucose measurements into MyChart flowsheets during implementation period & follow-up period (dichotomous), (b) mean number of flowsheet entries during implementation period and follow-up period (c) fraction of patients for whom order is placed by doctor

Hypothesis: Additional reminder messaging to patients that (1) emphasizes the value of tracking blood glucose data to the patient OR (2) emphasize the value of tracking blood glucose data to the doctor OR (3) informs patient of their selection for a chance to receive an award conditional on tracking will increase adoption relative to no reminder messaging.

Outcome Measure: Comparison of individuals across reminder messaging assignment groups (within treatment practices)-- (a) fraction of patients entering blood glucose measurements into MyChart flowsheets during implementation period & follow-up period (dichotomous), (b) mean number of flowsheet entries during implementation period and follow-up period

Hypothesis: Promotion of adoption of electronic blood glucose tracking through the means described above will result in the following intent-to-treat effects:

(a) reduction in patient A1c

Outcome Measures: Intent to treat comparison of individuals between treatment and control practices of the following measures at the end of the intervention period and follow-up period: (1) Mean A1c (2) Quartiles of A1c using quantile regression analysis (3) fraction of patients experiencing improvement [reduction] in A1c from baseline (dichotomous) (4) fraction of patients below benchmark 7.0% A1c (dichotomous)

(b) increase in frequency of doctor-patient interaction

Outcome Measures: Intent to treat comparison of individuals between treatment and control practices of the following measures during the intervention period and follow-up period: (1) number of securing messaging (2) number of phone interactions, and (3) number of in-office appointments

(c) changes to treatment plan path

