Outcome Measure: Intent to treat comparison of individuals between treatment and control practices of number of alterations to patient prescriptions/medication list during the intervention period and follow-up period

Hypothesis: Reminder messaging treatments that induce more intensive use of flowsheets will lead patients to experience larger effects as described above.

Outcome Measure: Intent to treat and treatment on the treated comparison of individuals across reminder messaging assignment groups (within treatment practices)-- reduction in A1c, increase in frequency of doctor-patient interactions, changes to treatment plan path (outcomes as described above in a-c)

Hypothesis: Entries of blood glucose data will be predictive of A1c and will lower over the study period.

Outcome Measure: Descriptive analysis of flowsheet entry values in the treatment group during the implementation and follow-up period.

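### The secure-message count in 3.4 has no rule on the study's own secure messages; if all are counted, patients with an order differ by 6 v 0 between reminder conditions before behaviour changes

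*Combined protocol and SAP*

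**What the plan says.** Hypothesis 1.2.3(b) predicts more frequent contact between doctor and patient. Section 3.4 measures this, between treatment and control practices, by "1) number of securing messaging (2) number of phone interactions, and (3) number of in-office appointments", over the intervention and follow-up periods. Nothing says whose messages count, in which direction, or whether any are left out.

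For hypothesis 1.2.4, Section 3.4 reuses the same outcomes in an "Intent to treat and treatment on the treated comparison of individuals across reminder messaging assignment groups (within treatment practices".

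Section 3.1.2 defines the reminder conditions for treatment-practice patients who have a flowsheet order:

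- Condition 1: "1) No additional reminders from research group".
- Condition 2: "2) Standard secure message reminder, addressed from Inova Medical Group, sent every two weeks during 12 week implementation period".
- Condition 3: the same schedule, from Inova, with the chance of a gift card.
- Condition 4: "4) Secure message reminder, addressed from primary care doctor, sent every two weeks during 12 week implementation period".

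The research team runs all four conditions. The same section adds: "The number of reminder conditions may be reduced (to 2 or 3 instead of 4) depending on the rate of flowsheet orders by physicians".

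Section 3.1.1 adds one earlier message in treatment practices: "providers will be given text for a secure smart-text message to send to all patients receiving the flowsheets". Control practices get no encouragement (Section 3.2).

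Section 4.2 says that the outcome datasets will come from queries still to be built, and describes no filter on messages.

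**The concern.** The outcome and the intervention are recorded in the same place. A plain count of secure messages in the record would include the reminders, so part of the outcome is fixed by assignment. Neither the covariates nor the practice-clustered standard errors of Section 4.2 can remove this, because the assignment itself creates the difference.

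Two conclusions are at stake. Under 1.2.4, a reminder condition could appear to raise contact between doctor and patient when all that has been counted is the reminders. Under 1.2.3(b), treatment practices could appear to have more contact than control practices for the same reason, and this could be read as a mechanism behind a health effect.

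The counting window is also loose. Section 3.4 refers to an intervention period, but the timetable in Section 2.3 has baseline, administration, implementation and follow-up periods and no period of that name. It is therefore unclear whether a smart-text sent in the two-week administration period falls inside the count.

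**Working it through.** The documents give no expected value, SD or power for the message count, so there is no planned figure to reproduce. The check is arithmetic on the plan's own schedule.

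**Inputs.** One reminder per two weeks for 12 weeks (Sections 3.1.2 and 2.3); 3,600 treatment-practice patients and four arms (Section 4.1); 900 per arm if the arms are equal, which is an assumption because assignment is by surname. The order rate is not given; 50% and 100% are used as assumed values.

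**Step 1: study reminders per patient with an order.** 12 / 2 = 6 in each of conditions 2, 3 and 4, and 0 in condition 1. (It would be 7 if one went out at both the start and the end of the 12 weeks.)

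**Step 2: built-in differences under three readings of the measure.** The last column averages over four equal conditions, with the total including one smart-text in brackets.

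| Messages counted | Cond. 1 | Cond. 2 and 3 | Cond. 4 | Treatment minus control, per patient with an order |
|---|---|---|---|---|
| All secure messages | 0 | 6 | 6 | 6 x 3/4 = 4.5 (5.5) |
| Addressed from the doctor | 0 | 0 | 6 | 6 x 1/4 = 1.5 (2.5) |
| Actually sent by a clinician | 0 | 0 | 0 | 0 (1) |

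The smart-text is common to all reminder conditions, so it affects only the between-practice comparison.

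**Step 3: fewer conditions.** If one of the retained conditions is no reminder, the all-messages reading gives 6 x 2/3 = 4.0 reminders with three equal conditions and 6 x 1/2 = 3.0 with two. The from-the-doctor reading gives 0 if condition 4 is dropped, 6 x 1/3 = 2.0 if it is one of three, and 3.0 if it is one of two.

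**Step 4: would a 6-message gap be significant?** The gap misses two-sided 5% significance only if SD > 6 / (1.96 x sqrt(2/n)).

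- 50% orders, n = 450 per arm: 6 / (1.96 x 0.0667) = 45.9.
- 100% orders, n = 900 per arm: 6 / (1.96 x 0.0471) = 64.9.

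No clustering term is used, because reminders vary within practices.

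**Step 5: comparing all treatment-practice patients by reminder group.** The gap is then 6 x order rate. At 50% it is 3.0 with 900 per arm, and the break-even SD is 3 / (1.96 x 0.0471) = 32.5.

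**Step 6: between practices, averaged over all treatment-practice patients.** The Step 2 and 3 figures scale with the order rate. For reminders alone under the all-messages reading, 50% orders gives 0.5 x 4.5 = 2.25 with four conditions, 2.0 with three and 1.5 with two. No significance probability is given here, because the SD and intra-cluster correlation of message counts are not in the documents.

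**After the fix.** With study messages removed, the built-in difference is 0 v 0 between reminder conditions. Between practices it is 0 without the smart-text, or at most 1 per patient with an order if the smart-text is kept.

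**The case against.** The strongest reply is that the measure stands under the label of doctor-patient interaction. Conditions 2 and 3 are addressed from the organisation, and the research team sends all the reminders, so a sensible analyst would not count them. On that reading the reminder conditions do not differ at all. This stands in part: 6 v 0 for all three conditions is one of three readings, and it applies to patients with an order. But the label is not a counting rule. Condition 4 goes out under the doctor's name, and a query by named sender would count it.

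A second reply concerns the smart-text. The provider sends it and it ends with "Please let me know if you have any questions", so in an intent-to-treat comparison of practices it is arguably real contact. That stands, and excluding it outright would be a preference and not a correction.

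A third is that Section 3.1.2 first calls the follow-up messages emails. This carries little weight: each active condition is then worded as a secure message, and Section 2.5 places all study communication in MyChart.

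A reader might go further and infer an order rate, and so an expected between-practice excess, from the effect sizes in Section 4.1. Those are minimum detectable effects, not forecasts, and do not support it. Nor can a treatment-on-the-treated bias be sized, since the plan states no method for that analysis. Section 1.1 makes the study of health effects conditional on increased adoption, but that condition does not clearly cover interaction counts, so it does not show that the order rate will be high when this outcome is tested.

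**Conclusion.** The concern holds as an undefined count with a material consequence. Applied literally, the measure counts the intervention as its own outcome: 6 v 0 per patient with an order for each of conditions 2 to 4 against condition 1, and 4.5, 4.0 or 3.0 reminders per patient with an order between practices under four, three or two equal conditions. In the reminder comparison this would almost certainly be significant with no behaviour change, since message SDs above about 46 to 65 would be needed to hide it.

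This rests on counting all secure messages, on equal arms and on the stated schedule being followed. A reader might infer that the bias is certain; the documents do not support that, because a query that removes study messages would have none. What they show is that the plan does not choose.

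Nor does the problem reach other outcomes. Phone contacts, appointments, medication changes, adoption and A1c are untouched by this mechanism, and Section 4.1 names adoption and mean A1c as the key outcomes. The point should be fixed before the extract is built, but it does not threaten the main comparisons.

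**What to change.** In Section 3.4, define the measure as the number of individual secure messages between patient and clinician, excluding study-generated messages, meaning the reminders of conditions 2 to 4 and the gift-card notices. Use the same definition for hypothesis 1.2.4.

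- Log study messages when they are sent, so that the query can remove them.
- Report the between-practice count with and without the provider-sent smart-text.
- Add a count of patient-sent messages only, as a sensitivity analysis.
- State the counting window in the period names of Section 2.3.

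The cost is one definition, a send log and a filter in an extract that has yet to be built. The design and sample size do not change. Two limits remain. Smart-texts may not separate perfectly from other provider messages. Replies to study messages may also stay in the count, since the smart-text invites questions and Section 6.2 states that replies are disabled only for the gift-card notice.

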1.2 Hypotheses

1.2.1 Interfacing with primary care practices to encourage physicians to implement default online orders of blood glucose flowsheets and informational messaging for all patients with diabetes will increase patient adoption (as defined above).

1.2.2. Additional reminder messaging to patients that (1) emphasizes the value of tracking blood glucose data to the patient OR (2) emphasize the value of tracking blood glucose data to the doctor OR (3) informs patient of their selection for a chance to receive an award conditional on tracking will increase adoption relative to no reminder messaging.

1.2.3 Promotion of adoption of electronic blood glucose tracking through the means described above will result in the following intent-to-treat effects:

- (a) reduction in patient A1c
- (b) increases in frequency of doctor-patient interaction
- (c) changes to treatment plan path

1.2.4 Reminder messaging treatments that induce more intensive use of flowsheets will lead patients to experience larger effects as described in 1.2.3.

1.2.5 Entries of blood glucose data will be predictive of A1c on average and will lower over the study period.

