2. **Learn how:** See [insert link to instructions/screenshots] to learn how to use the electronic blood glucose flowsheets on MyChart
3. **Link your devices:** You don't need to have special equipment to use the flowsheets, but if you have an Apple/iOS device and compatible glucometer, you can set up automatic data transfer. This will pull the results of your glucose tests into MyChart automatically, making it even easier to track. See [insert link to instructions] for help setting this up, and for a list of compatible devices.
4. **Track your blood glucose:** For the next 3 months, try to enter at least 6 measurements total per week, spread out over a few different days. However, don't be discouraged if you miss a day-- even tracking occasionally could be beneficial to your health.

Note: If you've never tested your blood glucose before, get in touch with [Practice Contact] to make sure you have all the materials and instructions you need, and to confirm that testing is right for you. Patients who think they might be pregnant should also be sure to talk to a physician before starting any new tracking regime.

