3.2 Control Group

The control group will be randomly selected half of the 27 primary care practices, and will receive no encouragement of adoption. However, this group will not be explicitly discouraged from making flowsheet orders.

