5.2 Benefits

The intervention seeks to test methods for increasing utilization of an existing feature of the MyChart EHR system. Lessons from this aspect of the study may be applied to increase awareness and utilization of other new EHR features, potentially benefiting patients and doctors indirectly.

Patients who decide to track their blood sugar through MyChart as a results of the intervention may experience increased ability to control and manage their diabetes. Because providers will be able to view and interpret blood glucose data more easily and frequently, they may be more likely to adjust and tailor treatment plans to this information. Both of these factors may lead to improved patient health indicators (specifically A1c).

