6.1 Costs

There are no direct costs to participants. Indirect costs to patients may include inconvenience of receiving additional secure messages. Due to encouragement of flowsheet orders by physicians in the treatment group, patients choosing not to follow their doctor's recommendation of electronic glucose tracking may feel guilt, and patients choosing to complete the online flowsheets will need to spend additional time entering their values. Amount of time spent will depend on whether they set up an automatic download of electronic readings through their smartphone, or manually enter the values via an internet-connected device. If patients choose to start tracking their blood glucose and have not already been doing so, they may face additional supply costs.

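### The measure for 'changes to treatment plan path' counts every medication-list alteration, which adds noise to a question about glycemic treatment and could, if testing supplies are listed, also count supply orders

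*Combined protocol and SAP*

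**What the plan says.** Hypothesis 1.2.3 lists, as one intent-to-treat effect of promoting tracking, "c) changes to treatment plan path". Section 3.4 gives it a single measure, compared between treatment and control practices: the "number of alterations to patient prescriptions/medication list during the intervention period and follow-up period". The same outcome is used again in section 3.4 to compare the reminder groups within treatment practices. Neither section 3.4 nor section 4.2 names a drug class, separates starts, stops, dose changes and renewals, or says how testing supplies are handled.

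The purpose is described elsewhere. Section 1.3 relies on a structured-testing study in which access to readings led physicians to act on glycemia sooner and more often. Section 5.2 says of providers who can see the data that "they may be more likely to adjust and tailor treatment plans to this information".

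Three other places bear on supplies:

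- The draft launch message in section 3.1.1, written for treatment practices, says: "If you need help learning how to measure your blood glucose or getting testing supplies, you can contact [Practice Contact". It tells first-time testers to get in touch with the practice "to make sure you have all the materials and instructions you need".
- Section 6.1 says of patients who newly start tracking that "they may face additional supply costs".
- Section 3.2 says the control group "will receive no encouragement of adoption".

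**The concern.** This is the only outcome that looks directly at whether doctors change what they prescribe, and section 1.1 promises to consider the mechanisms by which health indicators do or do not improve. With an all-medication count, a short antibiotic course weighs the same as a change in glucose-lowering therapy. Two consequences follow.

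1. **Noise.** Unrelated changes enlarge the variance of the count in both arms, so a real change in glycemic prescribing is harder to detect, and any effect stated as a ratio looks smaller.
2. **Supplies (conditional).** If meters, strips or lancets are entered as prescriptions or list items, the launch message can add alterations in the treatment arm only. Randomization does not remove this, because the intervention itself would cause it.

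A null result could then hide a real change in prescribing, and a positive one could be taken for a change in medication when it partly reflects supply orders.

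**Working it through.** **No stated figure for this outcome.** Section 4.1 gives power for adoption and mean A1c only. As a check on the cluster set-up, I reproduced the A1c figure with 12 practices of 300 patients per arm (7200 patients in 24 practices, equal split assumed), SD 1.39, ICC 0.07 and baseline correlation 0.80. Two-sided 5% and 80% power are my assumptions.

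- Design effect = 1 + 299 × 0.07 = 21.93.
- SE = √(2 × 1.39² × (1 − 0.80²) × 21.93 / 3600) = 0.0921.
- Minimum detectable effect = (2.074 + 0.858) × 0.0921 = 0.270 using t with 22 df (0.258 using normal quantiles), against 0.27 stated.

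The same set-up is used below.

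**Noise from unrelated changes.** All rates here are assumed. Let g be glucose-lowering changes and u unrelated changes per patient over the 24 weeks of implementation plus follow-up (section 2.3), with Poisson counts and a true 20% rise in g only.

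- Absolute difference: d = (1.2g + u) − (g + u) = 0.2g. The term u cancels, so d is the same on either count. For g = 0.6, d = 0.12.
- Rate ratio on the planned count = (1.2g + u)/(g + u).
- SE = √[(2g + d + 2u)/3600 × (1 + 299 × ICC)]. The design effect is 3.99 at ICC 0.01 and 15.95 at ICC 0.05.
- Power = Φ(d/SE − 1.96).

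For g = 0.6:

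| u | Rate ratio | Power, ICC 0.01 | Power, ICC 0.05 |
|---|---|---|---|
| 0 (restricted count) | 1.20 | 88% | 35% |
| 0.6 | 1.10 | 62% | 20% |
| 1.5 | 1.06 | 41% | 14% |
| 3.0 | 1.03 | 27% | 10% |

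Example, first row, ICC 0.01: SE = √(1.32/3600 × 3.99) = 0.0382; 0.12/0.0382 = 3.14; Φ(3.14 − 1.96) = 0.88. Last row: SE = √(7.32/3600 × 3.99) = 0.0901; 0.12/0.0901 = 1.33; Φ(1.33 − 1.96) = 0.27.

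With g = 0.3 the pattern is the same from a lower start. Power is 60% restricted and 26%, 15% and 10% as u grows (ICC 0.01), or 20% falling to 10%, 7% and 5% (ICC 0.05).

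**Supplies, if they are listed.** Suppose therapy does not change at all. Extra alterations per treatment-arm patient = uptake × share needing supplies × items listed. For uptake I borrowed two figures from section 4.1 as anchors: 9.5% (the practice-level minimum detectable effect) and 20% (the assumed no-reminder adoption rate). Share (25% to 100%) and items (1 to 3) are assumed.

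- Lowest: 0.095 × 0.25 × 1 = 0.02. Highest: 0.20 × 1 × 3 = 0.60.
- Over assumed control totals of 0.9 to 3.6 alterations, the apparent rate ratio runs from 1 + 0.024/3.6 = 1.01 to 1 + 0.60/0.9 = 1.67.
- A middle case, 0.20 × 0.5 × 3 = 0.30, gives 1.08 to 1.33.
- With 20% uptake, one in five of those needing supplies and three items each, the addition is 0.20 × 0.20 × 3 = 0.12. That equals the true therapy effect assumed above, so the planned count could not tell the two apart.

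If supplies are not listed, every figure in this last part is zero.

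**The case against.** - **Unrelated drugs cause no bias.** A reader might infer that unrelated drugs pull the estimated effect towards zero. They do not on the difference scale: randomization balances them in expectation, and section 4.2 specifies regression without committing to a ratio. This objection stands. The cost is lost precision and, on a ratio scale only, a smaller-looking effect.
- **The supplies route rests on an unstated fact.** A reader might infer that the launch message will inflate the treatment-arm count. The documents do not say that supplies reach the prescription or medication list. Section 6.1 fits supplies bought by the patient equally well, and it concerns only patients not already testing. This stands, so the point is conditional.
- **Supply orders are not plainly spurious.** Section 5.1 describes self-monitoring as a treatment that is recommended in diabetes, so adding testing for someone who had none may be a change of plan in the protocol's own terms. This stands too, and is why supplies should be counted separately and reported, not discarded.
- **The hypothesis is broad.** Hypothesis 1.2.3(c) names no drug class. That is true, but the rationale in sections 1.3 and 5.2 is treatment adjusted to glucose data, and a count of all drugs answers that question poorly.
- **Little depends on it.** Section 4.1 treats adoption and mean A1c as the key outcomes, and section 1.1 makes the health analyses conditional on increased adoption. This limits the importance of the point without removing it.

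**Conclusion.** The concern holds as a matter of outcome definition. The planned count is wider than the mechanism it is meant to test. That unrelated drugs add noise follows from the wording alone. How much is not derivable from the documents. Under the assumed rates with g = 0.6, power falls from about 88% to between 62% and 27% (ICC 0.01), or from about 35% to between 20% and 10% (ICC 0.05). These figures rest on Poisson counts, normal quantiles, equal arms and the same ICC for both counts.

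The supplies effect is a possibility only. If supplies are listed, it could be anywhere from negligible to large (apparent rate ratio 1.01 to 1.67). The documents do not support saying that the count is biased towards no difference, that it will be inflated in the treatment arm, or that supply orders are outside the treatment plan. The importance is low: this is an unpowered outcome, and the adoption and A1c comparisons are unaffected.

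**What to change.** In section 3.4(c), define the main measure as the number of starts, stops and dose changes of glucose-lowering medicines during the intervention and follow-up periods. Count glucose-testing supply entries separately, and report the all-medication count as a secondary description. Use the same definitions for the reminder-group comparison. State whether this EHR records testing supplies as prescriptions or medication-list entries.

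The cost is small. Section 4.2 says the EHR vendor has offered to build the outcome queries, so this is a class filter in that specification, with no change to the intervention, sample or data source. The downsides are that a drug-class list must be written, preferably before outcome data are extracted so that the choice is not made after the results are seen, and that medication changes outside glucose control appear only in the secondary count.
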